**Programming note:**

Parameters are uCreatine (uCr), uClusterin (uCLU) , uCystatin-C (uCysC), uKidney Injury Molecule-1 (uKIM-1), u N-Acetyl-beta-D-Glucosaminidase (uNAG), Neutrophil Gelatinase-Associated Lipocalin (uNGAL) and uOsteopontin (uOPN).

Keep the decimal places as exactly the same as what is shown in this table shells

Exten the table for visits Day 7, 14 and 21.

Table 14.3.5.4.2

Geometric Mean (GM) Composite Measure (CM) on Quantitative Biomarker Panel for Renal Tubular Injury Results by Study Visit  
Safety Population

Visit	Number of Subjects (N=xx)	GM CM
Baseline	xx	x.xx
Day 1	xx	x.xx
Day 7	xx	x.xx
Day 14	xx	x.xx
Day 21	xx	x.xx

GM CM = Geometric Mean (GM) Composite Measure (CM)

***Programming note:*** Update footnote to SOURCE: Listing 16.2.8.1.4

Table 14.3.6.1.1  
Summary of Vital Signs by Study Visit  
Safety Population

**Same shell as Table 14.3.5.1.1**

**Programming note:** Visits include Screening, Baseline, Day 1, Day 7 Pre-Dose, Day 7 Post-Dose, Day 14 Pre-Dose, Day 14 Post-Dose, and Day 21; parameters include Temperature (C), Respiration Rate (breaths per min), Systolic Blood Pressure (mmHg), Heart Rate (bpm), Diastolic Blood Pressure (mmHg), and Weight (kg); SOURCE: Listing 16.2.8.3.1, Listing 16.2.8.3.2.

Table 14.3.6.1.2  
Shift from Baseline in Vital Signs by Study Visit  
Safety Population

**Same shell as Table 14.3.5.1.2**

**Programming note:** Visits include Screening, Baseline, Day 1, Day 7 Pre-Dose, Day 7 Post-Dose, Day 14 Pre-Dose, Day 14 Post-Dose, and Day 21; parameters include Temperature (C), Respiration Rate (breaths per min), Systolic Blood Pressure (mmHg), Heart Rate (bpm), Diastolic Blood Pressure (mmHg), and Weight (kg); Add the following footnote: "Abnormal vital signs are as follows. CCI SBP >140 mmHg, SBP <90 mmHg, DBP >90 mmHg, DBP <60 mmHg, HR >100 bpm, HR <60 bpm, Respiration rate >20 breaths/min, Respiration rate <12 breaths/min, Oral temperature >99.1 °F/37.2 °C, Oral temperature <97.8 °F/36.5 °C" Update footnote to SOURCE: Listing 16.2.8.3.1, Listing 16.2.8.3.2

Table 14.3.6.1.3  
Summary of Orthostatic Vital Signs by Study Visit  
Safety Population

**Same shell as Table 14.3.5.1.1**

**Programming note:** Visits include Screening, Baseline, Day 1, Day 7 Post-Dose, Day 14 Post-Dose, and Day 21; parameters include Standing Systolic Blood Pressure (mmHg), Supine Systolic Blood Pressure (mmHg), Supine Heart Rate (bpm), Standing Heart Rate (bpm), Standing Diastolic Blood Pressure (mmHg), and Supine Diastolic Blood Pressure (mmHg); SOURCE: Listing 16.2.8.3.1, Listing 16.2.8.3.2.

Table 14.3.6.1.4  
Shift from Baseline in Orthostatic Vital Signs by Study Visit  
Safety Population

**Same shell as Table 14.3.5.1.2**

**Programming note:** Visits include Screening, Baseline, Day 1, Day 7 Post-Dose, Day 14 Post-Dose, and Day 21; parameters include Standing Systolic Blood Pressure (mmHg), Supine Systolic Blood Pressure (mmHg), Supine Heart Rate (bpm), Standing Heart Rate (bpm), Standing Diastolic Blood Pressure (mmHg), and Supine Diastolic Blood Pressure (mmHg); Update footnote to SOURCE: Listing 16.2.8.3.1, Listing 16.2.8.3.2

Table 14.3.6.1.5  
Summary of Orthostatic Vital Signs Shift from Baseline Categories by Study Visit  
Safety Population

Study Visit Shift Category	Cohort-1			Cohort-2		
	SBP [1] (N=XX) n (%)	DBP [1] (N=XX) n (%)	HR [1] (N=XX) n (%)	SBP [1] (N=XX) n (%)	DBP [1] (N=XX) n (%)	HR [1] (N=XX)
Day 7						
Shifted	XX (XX.X%)	XX (XX.X%)	XX (XX.X%)	XX (XX.X%)	XX (XX.X%)	XX (XX.X%)
Unshifted	XX (XX.X%)	XX (XX.X%)	XX (XX.X%)	XX (XX.X%)	XX (XX.X%)	XX (XX.X%)
Missing	XX (XX.X%)	XX (XX.X%)	XX (XX.X%)	XX (XX.X%)	XX (XX.X%)	XX (XX.X%)
Day 14						
Shifted	XX (XX.X%)	XX (XX.X%)	XX (XX.X%)	XX (XX.X%)	XX (XX.X%)	XX (XX.X%)
Unshifted	XX (XX.X%)	XX (XX.X%)	XX (XX.X%)	XX (XX.X%)	XX (XX.X%)	XX (XX.X%)
Missing	XX (XX.X%)	XX (XX.X%)	XX (XX.X%)	XX (XX.X%)	XX (XX.X%)	XX (XX.X%)
Day 21						
Shifted	XX (XX.X%)	XX (XX.X%)	XX (XX.X%)	XX (XX.X%)	XX (XX.X%)	XX (XX.X%)
Unshifted	XX (XX.X%)	XX (XX.X%)	XX (XX.X%)	XX (XX.X%)	XX (XX.X%)	XX (XX.X%)
Missing	XX (XX.X%)	XX (XX.X%)	XX (XX.X%)	XX (XX.X%)	XX (XX.X%)	XX (XX.X%)

Abbreviations: DBP= diastolic blood pressure (mmHg); HR = heart rate (bpm); SBP = systolic blood pressure (mmHg).

Note: Percentages are n/Number of subjects in the Safety Population and respective Protocol Amendment \* 100. Shift status is defined as a reduction in SBP of 20 mmHg or more, and/or a reduction in DBP of 10 mmHg or more, and/or an increase in heart rate >20 beats/min for the standing measurement compared to the supine or semi-supine measurement.

[1] The baseline value for each variable is the last observation recorded prior to the first dose of treatment.

SOURCE: Listing 16.2.8.3.2

**Programming note:** Repeat table for Overall.

Table 14.3.6.1.6  
Summary of Orthostatic Hypotension by Study Visit  
Safety Population

Study Visit Category	Cohort-1 (N=XX) n (%)	Cohort-2 (N=XX) n (%)	Overall (N=XX) n (%)
Baseline [1]			
Reduction of SBP of 20 mmHg or more	XX (XX.X%)	XX (XX.X%)	XX (XX.X%)
Reduction of DBP of 10 mmHg or more	XX (XX.X%)	XX (XX.X%)	XX (XX.X%)
Day 7 Post-Dose			
Reduction of SBP of 20 mmHg or more	XX (XX.X%)	XX (XX.X%)	XX (XX.X%)
Reduction of DBP of 10 mmHg or more	XX (XX.X%)	XX (XX.X%)	XX (XX.X%)
Day 14 Post-Dose			
Reduction of SBP of 20 mmHg or more	XX (XX.X%)	XX (XX.X%)	XX (XX.X%)
Reduction of DBP of 10 mmHg or more	XX (XX.X%)	XX (XX.X%)	XX (XX.X%)
Day 21			
Reduction of SBP of 20 mmHg or more	XX (XX.X%)	XX (XX.X%)	XX (XX.X%)
Reduction of DBP of 10 mmHg or more	XX (XX.X%)	XX (XX.X%)	XX (XX.X%)

Abbreviations: DBP = diastolic blood pressure; SBP= systolic blood pressure.

Note: Percentages are n/Number of subjects in the Safety Population and respective Protocol Amendment\*100. Orthostatic hypotension is defined as a reduction in SBP of 20 mmHg or more, and/or a reduction in DBP of 10 mmHg or more, for the standing measurement compared to the supine or semi-supine measurement.

[1] The average of the 3 baseline orthostatic vital signs measurements will be used for comparison to all post-treatment measurements.

SOURCE: Listing 16.2.8.3.2

Table 14.3.6.2.1  
Summary of 12-Lead Electrocardiogram by Study Visit  
Safety Population

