## **7.10       Orthostatic Vital Signs**

Orthostatic vital signs will be measured at Screening, Baseline, Day 1, Day 7, Day 14 and during the Follow-up visit.

During the Screening visit, orthostatic VS measurements will be done once, at any time during the visit.

During the Baseline/Pre-Dose visit, baseline orthostatic VS will include 3 separate measurements with each measurement of blood pressure and heart rate separated from the next by at least 15-20 minutes apart, to minimize the potential impact of biological variability of a single baseline measurement. The average of the 3 baseline orthostatic VS measurements will be used for comparison to all post-treatment measurements.

During Day 1, orthostatic VS measurements will be done twice, 2 to 4 hours following each in-clinic dose.

During Day 7 and Day 14 visits, orthostatic VS measurements will be done once, 2 to 4 hours following the in-clinic dose.

During the Follow-up visit, orthostatic VS measurements will be done once, at any time during the visit.

Orthostatic VS must be assessed using an appropriate device, and the arm position must be standardized for each subject. These measurements are to be taken in the same arm for the duration of the study. The position of the cuff on the arm should be in line with the heart with the arm lying next to the subject when semi-supine and should be in line with the heart at approximately a 45 degrees angle from horizontal for the standing measure.

In order to obtain orthostatic VS, the subjects will undergo the following procedures in sequential order:

1. The subject will rest in a supine or semi-supine position for at least 5 minutes.
2. After remaining supine or semi-supine for 5 minutes, one measurement of blood pressure and heart rate will be taken.
3. The subject will then be asked to sit on the edge of the bed/chair with feet on the floor (or with feet dangling from the bed/chair depending on the height of the bed/chair) for approximately 30 seconds.
4. The person performing the assessment will then ask the question, “Are you ready to stand?”
  - If the subject responds in the affirmative, the subject will proceed to stand and then be asked to remain standing for 2 minutes. After standing for 2 minutes, blood pressure and heart rate will be recorded.

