## 6. General Considerations for Statistical Analysis

### 6.1. Statistical Definitions and Algorithms

#### 6.1.1. Baseline

The last non-missing observed value recorded on or before the date of the first dose of treatment at the Pre-dose visit will be used as the baseline observation for all calculations of change from baseline.

Wearable sensor measurements of upper limb tremor will be captured at 2 different times during the Pre-dose visit (Visit 2); the average of the 2 assessments will be used as the baseline observation for all calculations of change from baseline in wearable sensor assessments.

During the Pre-dose visit, baseline orthostatic vital signs will include 3 separate measurements, and the average of the 3 (or fewer if missing data occur) baseline orthostatic vital signs measurements will be used as baseline for comparison to all post-treatment measurements.

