#### 6.1.8. Derived Variables

- **TETRAS-PS Total score** = sum of the 16 individual item scores (only the maximum of the item 5 lower limb tremor scores will be counted), with a maximum total score of 64. There will be no missing value imputation performed.
- **TETRAS-PS Upper Limb Subscale score** = sum of the item 4, item 6, item 7 and item 8 scores (forward outstretched postural tremor, lateral “wing beating” postural tremor, kinetic tremor, Archimedes spirals, and dot approximation task from both sides of the body, as well as handwriting), with a maximum total score of 44. There will be no missing value imputation performed.
- **TETRAS-PS Upper Limb Tremor (Item 4) Total score** = sum of the 6 individual scores under item 4 scores (forward outstretched postural tremor, lateral “wing beating”

postural tremor, and kinetic tremor scores for left and right hand, respectively) from both sides of the body, with a maximum total score of 24. There will be no missing value imputation performed.

Commercially Confidential Information

- **Kinesia Upper Limb Tremor score** = sum of the scores from the extended arms posture, wing-beating posture, and kinetic “finger-to-chin” wearable sensor maneuvers from both sides of the body, with a maximum total score of 24. There will be no missing value imputation performed.
- **Change from baseline** = value at current time point – value at baseline.
  - For calculation of change from baseline to Day 14 for discontinued subjects their assessment value at the early termination (ET) visit should be used
- **Percent change from baseline** = (change from baseline / baseline) \* 100. If both baseline and change from baseline are 0 then percent change from baseline will be set to 0.
- **Study day** = number of days relative to the first dose date of study drug and will be calculated using the following formulas:  
For pre-dose: study day= Start Date/ Stop Date – first dose date;  
For post-dose: study day= Start Date/ Stop Date – first dose date + 1.
- **TEAE (treatment-emergent AE)** = any AE with an onset date/time after the first dose of treatment. If an AE was present at baseline and worsened on or after the first dose of treatment it will be considered a TEAE.
- **Orthostatic hypotension** is defined as a reduction in SBP of 20 mmHg or more, and/or a reduction in DBP of 10 mmHg or more, for the standing measurement compared to the supine or semi-supine measurement.

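### SAP Table 14.3.6.1.5 is titled as a shift from baseline but classifies subjects on the same-visit standing-versus-supine difference, so it reports per-visit prevalence, and its baseline footnote contradicts the average-of-three rule

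*SAP*

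**What the plan says.** The SAP plans a table called "Summary of Orthostatic Vital Signs Shift from Baseline Categories by Study Visit" (Table 14.3.6.1.5, Safety population). It has rows Shifted, Unshifted and Missing at Days 7, 14 and 21, and separate SBP, DBP and HR columns within each cohort, repeated for Overall. It has no baseline row and no cross-classification against baseline.

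The note under the table gives the rule. For blood pressure it reads: "Shift status is defined as a reduction in SBP of 20 mmHg or more, and/or a reduction in DBP of 10 mmHg or more". A third criterion, for heart rate, is linked to these as a further alternative, and the sentence closes by naming the comparator for all three: "an increase in heart rate >20 beats/min for the standing measurement compared to the supine or semi-supine measurement". Footnote [1], attached to the column headings, reads: "The baseline value for each variable is the last observation recorded prior to the first dose of treatment".

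Elsewhere the plan defines the orthostatic baseline differently. SAP 6.1.1 states that "the average of the 3 (or fewer if missing data occur) baseline orthostatic vital signs measurements will be used as baseline", and SAP 9.3 says the same. Protocol 7.10 has: "The average of the 3 baseline orthostatic VS measurements will be used for comparison to all post-treatment measurements". The footnote to the next table, 14.3.6.1.6, also uses the average of three.

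SAP 6.1.8 defines orthostatic hypotension with the same two blood-pressure cut-offs and the same comparator, "for the standing measurement compared to the supine or semi-supine measurement".

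**The concern.** A shift from baseline needs two states per subject, one before dosing and one at the visit. The printed rule uses only the second. Someone whose blood pressure or heart rate already behaved this way on standing before the first dose is therefore reported as having shifted on treatment.

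This matters because the study has one arm and safety is its primary objective. SAP 9 names orthostatic changes among the safety evaluations, and Protocol 11.2.4 says each subject is assessed against their own baseline. There is no control group to show how often these criteria are met without the drug. A reader of the study report would take the Shifted count as new on treatment.

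Two further points affect programming. The rule joins three criteria with and/or while the table has one column per parameter, so the text does not say whether a column reflects its own criterion or any of the three. Footnote [1] also names a baseline that the rest of the plan rejects for these measurements.

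**Working it through.** The plan states no figure to reproduce. The check is whether the baseline value can change any cell.

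**Rule as printed** (SAP Table 14.3.6.1.5, note), applied at each visit:
- SBP: supine − standing ≥ 20 mmHg
- DBP: supine − standing ≥ 10 mmHg
- HR: standing − supine > 20 beats/min

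Every term comes from the same visit, so no baseline value appears.

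**Rule that the title implies**: criterion met at the visit and not met at baseline.

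**Both rules on invented values** (SBP in mmHg, supine/standing; the DBP and HR criteria are not met in any case):

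| Subject | Baseline | Fall | Day 14 | Fall | Change in fall | Printed rule | Baseline-referenced rule |
|---|---|---|---|---|---|---|---|
| A | 140/118 | 22 | 140/120 | 20 | −2 | Shifted | Not a shift |
| B | 140/138 | 2 | 140/121 | 19 | +17 | Unshifted | Not a shift |
| C | 140/138 | 2 | 140/118 | 22 | +20 | Shifted | Shifted |

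The rules disagree only on A, who met the criterion before dosing and whose fall then lessened slightly. They agree on C, the genuine new onset. B stays below the cut-off and is not counted by either.

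**What the other orthostatic outputs provide:**

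| Output | Baseline information | Gap |
|---|---|---|
| Table 14.3.6.1.3 | Change from baseline in standing and supine values | Not the postural difference |
| Table 14.3.6.1.4 | Low/normal/high category at baseline by category at visit, standing and supine separately | Not the postural criteria |
| Table 14.3.6.1.6 | Count meeting the SBP and DBP criteria at baseline and at Days 7, 14 and 21 | Marginal counts only; no heart rate |
| Listing 16.2.8.3.2 | Per-subject values, averages, standing–supine difference | Not summarised |

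If each column of Table 14.3.6.1.5 uses its own criterion, its SBP and DBP Shifted counts equal the Day 7, 14 and 21 counts of Table 14.3.6.1.6: same cut-offs, comparator and population. The table then adds only the heart-rate column. That criterion appears in neither Protocol 7.10 nor the visible text of SAP 6.1.8 and 9.3, and no planned table shown gives its baseline status.

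**Size per affected subject.** Protocol 11.2.4 plans approximately 30 subjects and SAP 3.2 up to 30. If the Overall column has n = 30, one subject is 1/30 = 3.3 percentage points. Cohort sizes are not given. Assuming 10 to 20 subjects in a cohort, one subject is 1/20 = 5 to 1/10 = 10 points.

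**The case against.** The strongest reply is that this is one descriptive shell and the information is mostly available elsewhere. The primary endpoint is treatment-emergent adverse events. Protocol 11.2.1 asks only for listing and flagging of out-of-range orthostatic blood pressure, and SAP 9.3 does not call for this particular classification. Table 14.3.6.1.6 lets a reader compare baseline with post-dose blood-pressure counts, and the listing allows any status to be derived. Exclusion criterion 19 bars subjects with a past history of orthostatic hypotension, so few should meet the blood-pressure criteria at baseline. Footnote [1] repeats wording from other shells and looks like carried-over text.

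Most of this stands, and it limits the consequence. It does not make the title and the rule agree. Marginal counts cannot show who newly met a criterion. No comparable exclusion is visible for a heart-rate rise on standing.

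Three stronger readings are tempting and should not be adopted:
- **The rule could hide a drug effect.** Anyone who newly meets a criterion is counted as Shifted, as subject C shows. Subject B is missed because of the cut-off, and a baseline-referenced rule with the same cut-offs misses B too.
- **Using one last reading instead of three makes the result noisier.** That concerns the variance of a change score. This table shows counts, and its rule uses no baseline, so the footnote alters no cell as printed.
- **All three columns must show the same number.** The literal and/or wording allows it, but with one criterion stated per parameter and one column per parameter, the natural reading is one criterion per column. The wording is ambiguous; identical columns are not the likely result.

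**Conclusion.** The point holds as a mislabelled safety output and a contradictory baseline footnote. As printed, Table 14.3.6.1.5 reports the prevalence of an orthostatic response at each visit. Subjects who already met a criterion at baseline and meet it again are counted as shifts, so the error can only be overcounting.

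The likely size is modest: 3.3 percentage points for each such subject if the Overall column has 30, and more within a cohort. The documents give no basis for saying how many there will be. For blood pressure the number is probably small, assuming exclusion 19 works as intended and baseline readings agree with history; for heart rate nothing visible limits it. The gaps left by the other planned tables are within-subject new onset for all three criteria and any baseline summary of the heart-rate criterion.

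The footnote contradiction stands separately. It has no numerical effect under the printed rule, but it would matter once the table makes a real comparison with baseline.

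**What to change.** - For SBP, DBP and HR separately, define Shifted as criterion not met on the averaged baseline (mean standing against mean supine over the three readings, or fewer if missing) and met at the visit. Alternatively, keep the printed rule, retitle the table as orthostatic response by visit, and add a baseline row covering all three criteria.
- State that each criterion applies to its own column, in place of the single and/or sentence.
- Replace footnote [1] with the average-of-three baseline. Check Tables 14.3.6.1.3 and 14.3.6.1.4 at the same time: they reuse laboratory shells carrying the same last-observation footnote, and their programming notes do not change it.
- Keep Table 14.3.6.1.6 as the same-visit count of orthostatic hypotension.

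The cost is shell and derivation text, with matching programming. No new data are needed, because the baseline readings are already scheduled and listed.

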### 9.3. Vital Signs

Descriptive summaries of observed values and changes from baseline will be calculated for supine systolic blood pressure (SBP), standing SBP, supine diastolic blood pressure (DBP), standing DBP, supine heart rate (HR), standing HR, respiration rate, and oral temperature by study visit for the Safety Population overall and by cohort. Shifts from baseline for SBP, DBP, and HR values below, within, or above the normal range will be provided by study visit for the Safety Population overall and by cohort. Vital sign parameters outside the normal range will be flagged in the listings. The mean change from baseline in each parameter will also be plotted by study visit. Abnormal vital signs are as follows:

Commercially Confidential Information

- SBP >140 mmHg
- SBP <90 mmHg
- DBP >90 mmHg
- DBP <60 mmHg
- HR >100 bpm
- HR <60 bpm
- Respiration rate >20 breaths/min
- Respiration rate <12 breaths/min
- Oral temperature >99.1 °F/37.2 °C
- Oral temperature <97.8 °F/36.5 °C

Orthostatic vital signs (blood pressure and heart rate) will also be summarized by position and study visit and by cohort. During the Pre-dose visit, baseline orthostatic vital signs will include 3 separate measurements and the average of the 3 baseline orthostatic vital signs measurements will be used for comparison to all post-treatment measurements. The average HR, SBP, and DBP will be presented in the pre-dose baseline summaries and each of the individual measurements will be listed for that study visit.

Orthostatic hypotension will be defined as a reduction in systolic blood pressure of 20 mmHg or more and/or a reduction in diastolic blood pressure of 10 mmHg or more, for the standing measurement compared to the supine or semi-supine measurement. The frequency and percentage of subjects with orthostatic hypotension will also be presented by cohort. Any confirmed orthostatic hypotension or clinically significant measurements that are associated with clinical symptoms will be recorded as AEs. Orthostatic vital signs parameters outside the ranges specified above will be flagged in the listings.

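### Table 14.3.6.1.6 compares an orthostatic hypotension rate based on the mean of three baseline readings with single-reading rates at later visits, which tilts the descriptive comparison toward an apparent rise

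*SAP*

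**What the plan says.** Protocol 7.10 takes three separate orthostatic measurements at Baseline/Pre-dose, at least 15 to 20 minutes apart, in order "to minimize the potential impact of biological variability of a single baseline measurement". It then states: "The average of the 3 baseline orthostatic VS measurements will be used for comparison to all post-treatment measurements".

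Later visits in the table have one measurement each:
- Days 7 and 14: "During Day 7 and Day 14 visits, orthostatic VS measurements will be done once, 2 to 4 hours following the in-clinic dose".
- Day 21: "During the Follow-up visit, orthostatic VS measurements will be done once, at any time during the visit".

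SAP 6.1.1 carries the averaging into the analysis: "the average of the 3 (or fewer if missing data occur) baseline orthostatic vital signs measurements will be used as baseline". SAP 9.3 says of the display: "The average HR, SBP, and DBP will be presented in the pre-dose baseline summaries". The individual baseline readings are only listed. The same section adds: "The frequency and percentage of subjects with orthostatic hypotension will also be presented by cohort".

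The shell of Table 14.3.6.1.6 has rows for Baseline, Day 7, Day 14 and Day 21. Each visit has one SBP row and one DBP row, with no combined row. Footnote [1], attached to the Baseline row, says: "The average of the 3 baseline orthostatic vital signs measurements will be used for comparison to all post-treatment measurements".

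OH is defined within a visit, standing against supine or semi-supine, with the same fixed cut-offs throughout (Protocol 7.10; SAP 6.1.8 and 9.3).

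**The concern.** Averaging the baseline is sound for a continuous change from baseline. A yes/no threshold behaves differently, because the proportion beyond a cut-off depends on the spread of the measurement as well as its centre. A three-reading mean has a narrower spread than one reading, so the two kinds of row have different expected percentages when nothing has changed in the subjects.

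The direction follows if the typical fall is smaller than the cut-off. That is likely here, because any lifetime history of OH is excluded (Protocol 4.2, criterion 19). The study has a single arm, safety is its primary objective, and about 30 subjects are planned. The table has no control column, so its Baseline row is the obvious comparator for the on-treatment rows. At this sample size one or two extra cases could make up most of what looks like a signal.

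**Working it through.** **What there is to reproduce.** The documents state no OH rate, no standard deviation (SD) of the postural fall and no power calculation. Every mean and SD below is an assumption. The cut-offs, reading counts and sample size come from the documents.

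**Model, no drug effect.** Let the postural fall have mean m and single-reading SD S. Let s be the share of the variance that is independent between readings at one visit. With cut-off c (20 for SBP, 10 for DBP):

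- one reading: P = 1 − Φ((c − m)/S)
- mean of three: P = 1 − Φ((c − m)/(S·√(1 − 2s/3))), because the variance is S²[(1 − s) + s/3]

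If m < c, the second probability is smaller whenever s > 0. The direction therefore does not depend on the particular values chosen.

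**Middle SBP case: m = 5, S = 10.** One reading: (20 − 5)/10 = 1.5, so P = 6.7%.

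| s | SD of mean of three | Baseline OH | Gap to 6.7% | Extra subjects per 30 |
|---|---|---|---|---|
| 0.25 | √83.3 = 9.13 | 5.0% | 1.7 points | 0.5 |
| 0.50 | √66.7 = 8.16 | 3.3% | 3.4 points | 1.0 |
| 0.75 | √50 = 7.07 | 1.7% | 5.0 points | 1.5 |

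**Range.** The grid used s of 0.25, 0.50 and 0.75. For SBP it took m of 0, 5 and 10 with S of 8, 10 and 12; for DBP, m of −5, −2, 0 and 2 with S of 5, 7 and 9.
- SBP row: gap of 0.3 to 8.3 points, or 0.1 to 2.5 subjects per 30.
- DBP row: gap of 0.1 to 8.3 points, or 0.03 to 2.5 subjects per 30.

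**How much shared noise matters.** Take SBP with mean 3, between-subject SD 6 and within-subject SD 8, and DBP with mean 0 and SDs 4 and 5.
- SBP, one reading: SD √(36 + 64) = 10, z = 1.70, P = 4.5%.
- SBP, mean of three, all within-subject noise independent: SD √(36 + 64/3) = 7.57, z = 2.25, P = 1.2%.
- SBP, mean of three, half that noise shared within the visit: SD √(36 + 32 + 32/3) = 8.87, z = 1.92, P = 2.8%.
- DBP, in the same order: 5.9% on one reading, 2.1% with independent noise, 4.0% with half shared.

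The artefact is about one subject per 30 in each row if the noise is fully independent, and about half a subject if half of it is shared. Readings 15 to 20 minutes apart plausibly share some of the day's level.

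**What one trial would show.** Trials of 30 were simulated 20,000 times, with the variance not independent between readings split 70/30 between subject and visit. In the middle SBP case with s = 0.50, the Day 7 count exceeded baseline in 62% of trials, equalled it in 22% and fell below it in 16%. All three later visits exceeded baseline in 34%. Across the grid the chance of a higher Day 7 count ran from 0.14 to 0.79 for SBP and from 0.04 to 0.79 for DBP.

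**The case against.** Several points on the other side have force.

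- **The footnote is not explicit.** It does not say that OH is classified on the averaged fall. That reading is an inference, though a natural one: the footnote sits on the Baseline row, SAP 9.3 puts averages in the baseline summaries, and source Listing 16.2.8.3.2 carries averaged standing and supine values and their difference. If another rule is intended, the SAP still has to state it.
- **Day 21 is a partial check.** It is also a single reading, about 7 days after the last dose. An averaging artefact should appear there as much as at Days 7 and 14, while a reversible drug effect would tend to recede. Carry-over is unknown, so the check is imperfect. A reader might infer that the table cannot distinguish artefact from signal at all; the Day 21 row shows that this goes too far.
- **The data can be recovered.** Listing 16.2.8.3.2 shows measurement number and an OH flag, so a like-for-like baseline count could be built. That lessens the harm but leaves the table as it is.
- **The table is descriptive.** No test of OH against baseline is planned in SAP 9.3, and the bias runs toward over-reporting harm. Both points lower the priority.
- **Repeat readings** are allowed when OH is suspected (Protocol 7.10). SAP 6.1.6 largely settles which counts, since a repeat is used only if the scheduled value is unavailable.

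**Conclusion.** The asymmetry is in the documents, and it biases the baseline-versus-treatment comparison in Table 14.3.6.1.6 toward an apparent rise in OH. This holds on the natural reading of the footnote and provided the mean fall is below the cut-off. The size is uncertain: roughly 0 to 2.5 extra subjects per 30 in each row under assumed variances, and less as more noise is shared between closely spaced readings.

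Three stronger conclusions that a reader might draw are not supported:

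- **That the table will show OH rising.** The bias is in expectation only, and in many null trials Day 7 would equal or fall below baseline.
- **That a several-fold inflation should be expected.** With the second set of assumptions above and an SBP–DBP correlation of 0.5, meeting either criterion gives 3.1% at baseline against 9.1% on one reading. The shell has no such combined row, and the baseline figure becomes 6.1% if half the within-subject noise is shared.
- **That the safety conclusions are compromised more widely.** Post-dose OH is judged within the visit, so the averaged baseline does not enter it. TEAEs and continuous changes from baseline are also unaffected. Only the Baseline row is lowered.

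I rate this minor to moderate: worth correcting before the table is produced, but not a condition for the analysis to proceed.

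**What to change.** In SAP 9.3 and Table 14.3.6.1.6, put the baseline OH percentage on the same footing as later visits, in one of two ways:

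1. Report the average of the three per-reading OH percentages. This uses all the data and matches the single-reading rate in expectation under no effect. The Baseline cell may then not be a whole number of subjects, so the shell needs a small change.
2. Classify baseline on one prespecified reading, for example the first. In the middle SBP case this gives 6.7% at both baseline and Day 7. The drawback is a noisier baseline percentage.

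Do not count a subject as having OH if any of the three baseline readings qualifies. That reverses the bias: in the middle SBP case baseline would be 12.8% to 17.3% against 6.7% afterwards.

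Keep the three-reading mean for continuous changes. Record the departure from Protocol 7.10 in SAP section 10, since the protocol prescribes the average for all post-treatment comparisons. In the same edit, reconcile the footnote of Table 14.3.6.1.5, which takes the last pre-dose observation as baseline, with the averaging rule in SAP 6.1.1.

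The cost is SAP wording, one derivation and a shell edit. No new data are needed.
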